**FINAL EVALUATION**

The final evaluation will ordinarily take place immediately following the last scheduled follow-up visit per the study protocol. It may also take place at any point the subject discontinues the study or is terminated from the study.

# Clinical Study Protocol

## Johnson & Johnson Vision Care, Inc.

Final Evaluation			
Step	Procedure	Details	[REDACTED]
F.1	Final Exam Form	Indicate if the subject completed the study successfully. If subject discontinued from the study, indicate the reason.	[REDACTED]
F.2	Exit Refraction	Perform bare-eye subjective spherocylindrical refraction with a phoropter and record the best-corrected distance visual acuity (OD, OS, OU) to the nearest letter.  Note: This step is not necessary if the subject was exited due to screen failure.	[REDACTED]
F.3	Exit Slit Lamp Biomicroscopy (for subjects that are discontinued early)	FDA Slit Lamp Classification Scale will be used to grade the findings.  If the clearance of the fluorescein needs to be expedited, preservative-free rewetting drops or saline may be instilled. This step is not necessary if the subject was exited due to screen failure.  Note: This step is not necessary if the subject was exited due to screen failure, or if biomicroscopy was performed as part of the final follow-up visit procedures (i.e., immediately prior to the final evaluation).	[REDACTED]

### 7.3. Unscheduled Visits

If, during the investigation, a subject requires an unscheduled visit to the clinical site, the following information will be collected, as appropriate:

- Chief complaint prompting the visit. If the reason is an adverse event, the applicable eCRF for the adverse event must be completed and subject record completed as appropriate.
- Date and time of the visit and all procedures completed at the unscheduled visit.
- Review of adverse event and concomitant medications.
- Documentation of any test article dispensed or collected from the subject, if applicable.
- Slit lamp findings (using the Slit Lamp Classification Scale).

If the Investigator withdraws a subject from the study, the final study visit case report forms must be completed indicating the reason(s) why the subject was withdrawn. The subject record must be completed documenting the date and primary reason for withdrawal and the study CRA notified.

## Clinical Study Protocol

### Johnson & Johnson Vision Care, Inc.

Any ocular and non-ocular Adverse Events that are ongoing at the time of the study visit will be followed by the Investigator, within licensure, until they have resolved, returned to pre-treatment status, stabilized, or been satisfactorily explained. If further treatment i.e., beyond licensure is required, the subject will be referred to the appropriate health care provider.

The following information will be collected during an unscheduled visit.

Unscheduled Visit			
Step	Procedure	Details	
U.1	Reason for unscheduled visit	Indicate if the only reason for the visit is that the subject requires additional test articles. If the reason is other than resupply of previously dispensed lenses, specify the reason for the visit.	
U.2	Chief Complaints (if applicable)	Record the subject's chief complaints for reasons for the unscheduled visit.	
U.3	Adverse Events and Concomitant Medications Review (if applicable)	Review any changes to the subject's medical history or concomitant medications from the previous study visit. Record any changes, and any adverse events.	
U.4	Entrance VA (if applicable)	Record the entrance distance visual acuity (OD, OS) to the nearest letter.	
U.5	Subjective Spherocylindrical Refraction (if applicable)	Perform bare-eye subjective spherocylindrical refraction with a phoropter (adopt the maximum plus to maximum visual acuity (MPMVA) approach and use the duo-chrome test for binocular balancing) and record the best corrected distance visual acuity to the nearest letter (OD, OS).	
U.6	Slit Lamp Biomicroscopy (if applicable)	FDA Slit Lamp Classification Scale will be used to grade the findings. If the clearance of the fluorescein needs to be expedited, preservative-free rewetting drops may be instilled.	
U.7	Dispensing (if applicable)	If the subject requires additional lenses to complete the wear period and is eligible to do so, provide additional lenses per the dispensing instructions given in the detailed study procedures.	
U.8	Exit Visual Acuity (if applicable)	Record the subject's exit distance visual acuity (OD, OS) to the nearest letter.	

**NOTE: If the only reason for the unscheduled visit is that the subject requires additional test articles, only the dispensing information needs to be recorded.**

# Clinical Study Protocol

## Johnson & Johnson Vision Care, Inc.

### 7.4. Laboratory Procedures

Not Applicable

## 8. SUBJECTS COMPLETION/WITHDRAWAL

### 8.1. Completion Criteria

Subjects are considered to have completed the study if they:

- provided informed consent.
- they are eligible.
- completed all study visits

### 8.2. Withdrawal/Discontinuation from the Study

A subject will be withdrawn from the study for any of the following reasons:

- Subject withdrawal of consent.
- Subject not compliant to protocol
- Subject lost to follow-up.
- Subject no longer meets eligibility criteria (e.g. the subject becomes pregnant).
- Subject develops significant or serious adverse events necessitating discontinuation of study lens wear
- Subjects who have experienced a Corneal Infiltrative Event (CIE).
- Investigator's clinical judgment regarding the subject safety reasons (that it is in the best interest of the subject to stop treatment).
- Subject not compliant with study lens wear schedule
- Subject not successfully dispensed due to lack of efficacy and safety including poor vision, poor comfort or unacceptable fit.

For discontinued subjects, the Investigator will:

- Complete the current visit (scheduled or unscheduled).
- Complete the Final Evaluation, indicating the reason that the subject was discontinued from the study.
- Record the spherocylindrical refraction with best corrected distance visual acuity.
- Collect used test article(s) (worn or brought to the visit) from the subject and discard them, unless otherwise stated in section 7.2.
- Collect all unused test article(s) from the subject.
- Make arrangements for subject care, if needed, due to their study participation

Additional subjects will be enrolled if a subject discontinues from the study prematurely.

In cases where a subject is lost to follow-up, every possible effort must be made to contact the subject and determine the reason for discontinuation/withdrawal. The measures taken to follow up must be documented including two written attempts and a certified letter (or equivalent) as the final attempt.

# Clinical Study Protocol

## Johnson & Johnson Vision Care, Inc.

### 9. PRE-STUDY AND CONCOMITANT INTERVENTION/MEDICATION

Concomitant medications will be documented during screening and updated during the study. Disallowed medications and therapies are medications or therapies that contraindicate contact lens wear. See the Exclusion criteria for specific details.

#### 9.1. Systemic Medications

The following table lists the medications disallowed in this study.

Table 4: Disallowed systemic medications

Class of Drug	Common Indication(s)	Common Examples
Anticholinergics	Irritable bowel syndrome, Parkinson's disease, peptic ulcer, cystitis, nasal congestion, cold symptoms, overactive bladder, COPD	Bentyl, Spiriva, Atrovent, Hyosyne, Levsin, Symax Fastab, Symax SL, Homax SL, Cogentin, Transderm Scop, etc., ...
Oral Phenothiazines	Antipsychotic disorders (schizophrenia, mania)	Compazine, Mellarill, Thorazine, Phenagran, etc....
Oral Retinoids	Cystic acne	Isotretinoin
Corticosteroids	Arthritis, colitis, asthma, bronchitis, allergic or inflammatory conditions	Cortisone, Prednisone, Hydrocortisone, Medrol, Kenalog etc., ...
Oral Tetracycline	Urinary Tract Infection, acne, chlamydia, gonorrhea	Sumcycin, Acitsite, Achromycin V, etc.

### 10. DEVIATIONS FROM THE PROTOCOL

Investigator will notify study sponsor upon identification of a protocol deviation. Protocol deviations must be reported to the sponsor within 24 hours after discovery of the protocol deviation. The Investigator will report deviations per IRB/IEC requirements. All deviations will be tracked, and corrective actions implemented as appropriate.

If it becomes necessary for the Investigator to implement a deviation in order to eliminate an immediate hazard to the trial subject, the Investigator may implement the deviation immediately without notification to the sponsor. Within 24 hours after the implemented deviation, the Investigator must notify and provide the rationale to the Sponsor and as required, to the IEC/IRB.

If the deviation potentially impacts the safety of patient or changes the technical integrity of the study, then it must be reported to IEC/IRB. This is a "Major Deviation". Deviations that contradict the information contained in the Informed Consent/Assent forms will be considered Major Deviations.

# Clinical Study Protocol

## Johnson & Johnson Vision Care, Inc.

Minor deviations have no substantive effect on patient safety or technical integrity of the study. They are often logistical in nature.

Protocol waivers are prohibited.

Table 5 lists examples of deviations that will constitute major and minor protocol deviations for this study.

Table 5: Examples of major and minor protocol deviations

Deviation category	Major deviation	Minor deviation
Out-of-window visit	Visit attended more than 2 days out of visit t window defined in study procedures	Visit attended 2 or fewer days out of visit window defined in study procedures
Unanswered PRO questions	For questionnaires where data is related to a primary or secondary endpoint, more than 2 PRO questions are unanswered (i.e., left blank).	For questionnaires where data is related to a primary or secondary endpoint, 2 or fewer PRO questions are unanswered (i.e., left blank).  For questionnaires where data where data is not related to a primary or secondary endpoint, any PRO questions are unanswered (i.e., left blank).

### 11. STUDY TERMINATION

The occurrence of one or more Unanticipated Serious Adverse Device Effect (USADE), or any SAE where the relationship to study agent cannot be ruled out, may result in stopping further dispensing of test article. In the event of a USADE or SAE, the Sponsor may unmask the treatment regimen for the subject(s) and will discuss this with the Investigator before any further subjects are enrolled.

The Sponsor will determine when a study will be stopped. The Principal Investigator always has the discretion to initiate stopping the study based on patient safety or if information indicates the study's results are compromised.

JJVC reserves the right to terminate the study at any time for any reason. Additionally, the IEC/IRB reserves the right to terminate the study if an unreasonable risk is determined. The study can be terminated by the Principal Investigator at the individual clinical site due to specific clinical observations, if in their opinion, after a discussion with JJVC, it is determined that it would be unwise to continue at the clinical site.

# **Clinical Study Protocol**

## **Johnson & Johnson Vision Care, Inc.**

JJVC (and the IEC/IRB and DMC, if applicable) will evaluate all adverse events. If it is determined that an adverse event presents an unreasonable risk, the investigation, or that part of the investigation presenting the risk, will be terminated as soon as possible.

Should the study be terminated (either prematurely or as scheduled), the Investigator will notify the IEC/IRB and Regulatory Authority as required by local regulatory requirements.

### **12. PROCEDURE FOR HANDLING PRODUCT QUALITY COMPLAINTS**

A Product Quality Complaint (PQC) refers to any written, electronic, or oral communication that alleges deficiencies related to the identity, quality, durability, reliability, safety, effectiveness or performance of test articles after they have been released for clinical trial use.

Potential complaints may come from a variety of sources including but not limited to subjects, clinical research associates (CRA), clinical operations managers (COM), medical monitors, and site personnel, etc. The following are not considered product quality complaints:

- Subject satisfaction inquiries reported via “Subjective Questionnaires” and “Patient Reported Outcomes (PRO).”
- Clinical test articles that are stored improperly or damaged after receipt at the investigational site.
- Lens replacements that occur due to drops/fall-outs.
- Damage deemed by clinicians or clinical staff to be caused by handling by the user, and not indicative of a quality deficiency (i.e. tears, rips, etc.), only in situations where there is no deficiency alleged by the subject.

Within 24 hours of site personnel becoming aware that a PQC has occurred, the PQC must be recorded in the EDC system, which will trigger an automatic email notification to the appropriate COM/CRA and Clinical QA representative. In cases where the EDC system in use is not configured to send automatic notifications or when an EDC system is not used, the COM/CRA is responsible for notifying Clinical QA upon discovery that a PQC has occurred.

Upon receipt of the EDC notification, the COM/CRA will contact the study site to collect additional information which will include:

- Date the complaint was received/recorded in the EDC System (Date of Sponsor Awareness).
- Who received the complaint.
- Study number.
- Clinical site information (contact name, site ID, telephone number).
- Lot number(s).
- Unique Subject Identifier(s).
- Indication of who first observed complaint (site personnel or subject).
- OD/OS indication, along with whether the lens was inserted.
- Any related AE number if applicable.

# Clinical Study Protocol

## Johnson & Johnson Vision Care, Inc.

- Detailed complaint description (scheduled/unscheduled visit, wear time, symptoms, resolution of symptoms, etc.).
- Eye Care Provider objective (slit lamp) findings if applicable.
- Confirmation of product availability for return (and tracking information, if available), or rationale if product is not available for return [REDACTED]

Once a complaint is received, it will be assessed by the COM, CRA, or trained site personnel to determine if it is an Adverse Event/Serious Adverse Event (AE/SAE). If the complaint results in an AE/SAE, the COM/CRA, or trained site personnel will follow section 13 of this protocol. If the AE/SAE was potentially the result of a product quality related deficiency, these procedures also apply and will be executed in parallel.

In some cases, a PQC form may be generated in EDC by the site in error. In this event, the PQC forms will be marked “Intentionally Left Blank” or “ILB”. Justification for ILB must be documented.

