### 13.2. Assessing Adverse Events

In conjunction with the medical monitor, the Investigator will evaluate adverse events to ensure the events are categorized correctly. Elements of categorization will include:

- Seriousness/Classifications (see definition in section 13.1).
- Causality or Relatedness – i.e. the relationship between the test article, study treatment or study procedures and the adverse event (not related, unlikely related, possibly related, or related - see definition in section 13.2.1).
- Adverse Event Severity – Adverse event severity is used to assess the degree of intensity of the adverse event (mild, moderate, or severe - see definition in section 13.2.2).
- Outcome – not recovered or not resolved, recovering or resolving, recovered or resolved with sequelae, recovered or resolved, death related to adverse event, or unknown.
- Actions Taken – none, temporarily discontinued, permanently discontinued, or other.

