#### 13.2.1. Causality Assessment

**Causality Assessment** – A determination of the relationship between an adverse event and the test article. The test article relationship for each adverse event should be determined by the investigator using these explanations:

- Not Related- An adverse event that is not related to the use of the test article, study treatment or study procedures.

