# Clinical Study Protocol

## Johnson & Johnson Vision Care, Inc.

### 13.4. Reporting Adverse Events

The Investigator will notify the Sponsor of an adverse event by e-mail, facsimile, or telephone as soon as possible and no later than 24 hours from discovery for any serious /significant adverse events, and 2 days from discovery for any non-significant adverse event. In addition, a written report will be submitted by the Principal Investigator to the IEC/IRB according to their requirements (section 13.4.2). The report will comment whether the adverse event was considered to be related to the test article, study treatment or study procedures.

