**Clinical Study Site:** Location where a clinical study is conducted, such as a doctor's office, university, or laboratory. Clinical studies are conducted by Investigators who are individual(s) responsible for the conduct of the clinical study at a study site. If a study is conducted by a team of individuals, the Investigator is the responsible leader of the team and may be called the Principal Investigator.

**Clinical Operations Manager (COM):** The Johnson & Johnson Vision Care (JJVCI) individual responsible for the overall management of a clinical trial.

**Monitor:** An individual designated to oversee the progress of a clinical study and ensure that it is conducted, recorded, and reported in accordance with the protocol, Standard Operating Procedures (SOPs), Good Clinical Practice (GCP), and applicable regulatory requirements.

**Medical Safety Officer (MSO):** Physician who has primary accountability in their product portfolio for product health and safety, and who serves as an independent medical voice for patient safety.

**Safety Management Team (SMT):** A cross-functional, collaborative team responsible for review, assessment and evaluation of medical safety data arising from any source throughout the product life cycle.

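### Section 12 lets the operations manager, the CRA or trained site staff alone decide whether a product complaint is an AE/SAE, with no Investigator role, time limit or check on a negative call, and is not reconciled with 13.2

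*Combined protocol and SAP*

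**What the plan says.** Section 12 defines a product quality complaint broadly enough to cover alleged deficiencies in the lens's safety, and the information gathered on each one includes symptoms and, where applicable, slit lamp findings. It then sets three steps that matter here.

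- Recording: "Within 24 hours of site personnel becoming aware that a PQC has occurred, the PQC must be recorded in the EDC system". This limit covers the recording only.
- Determination: "it will be assessed by the COM, CRA, or trained site personnel to determine if it is an Adverse Event/Serious Adverse Event (AE/SAE").
- Hand-off: "If the complaint results in an AE/SAE, the COM/CRA, or trained site personnel will follow section 13 of this protocol".

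Appendix I, section 3.0, describes the clinical operations manager (COM) as the sponsor's "individual responsible for the overall management of a clinical trial". Attachment A to that appendix lists the CRA in the sponsor's study team.

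Section 13.2 places the assessment elsewhere: "In conjunction with the medical monitor, the Investigator will evaluate adverse events to ensure the events are categorized correctly". The first element listed there is "Seriousness/Classifications (see definition in section 13.1"). Section 13.2.1 adds: "The test article relationship for each adverse event should be determined by the investigator using these explanations". Section 13.4 requires the Investigator to notify the sponsor "no later than 24 hours from discovery for any serious /significant adverse events", and within 2 days for non-significant events.

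**The concern.** Deciding whether a complaint with symptoms or slit lamp findings is an adverse event, and whether that event is serious, is a clinical judgment. Section 12 allows a person in trial management or monitoring to make it alone, about the sponsor's own lens. Section 13 is invoked only after a positive answer, so a wrong negative answer has no stated check within the complaint process. If that happened, a lens-related event could be recorded as a complaint only, or be reported later than 13.4 intends.

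**Working it through.** No sample size, power or event figure is involved, so the check sets the sections side by side.

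**Who decides seriousness.** Section 12 has the COM, CRA or trained site personnel determine whether the complaint is an SAE. Section 13.2 gives seriousness and classification to the Investigator with the medical monitor. Both address the same judgment and name different people, so here the sections conflict.

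**Who decides AE versus no AE.** Section 13.2 starts from events already identified as adverse. Section 12 covers the step before that and passes positive answers on. The sections do not state opposite rules, but nothing says who confirms the first step. This is a gap.

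**What follows a positive answer.** Section 12 says the COM/CRA or site personnel then follow Section 13. Section 13 assigns evaluation (13.2), causality (13.2.1), documentation (13.3) and notification (13.4) to the Investigator. It gives the COM and CRA no assessment or reporting task, so the hand-off is not fully specified.

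**What follows a negative answer.** No Investigator confirmation is required, nor any written reason. By contrast, Section 12 does require a documented justification when a complaint form was opened in error.

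**Categories.** Section 12 sorts only into AE and SAE. Section 13.1 also defines Significant Adverse Events, such as a contact lens induced peripheral ulcer. Sections 13.4 and 13.4.1 put these under the same 24-hour limit as serious events. The complaint step does not ask whether an event is significant.

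**Clock.** The limits in 13.4 run from discovery, and neither section says whether that means the site's awareness or the later determination.

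- If discovery is site awareness, and the assessment is made only when the recording allowance ends, the time left for a serious or significant event is 24 − 24 = 0 hours.
- If discovery is the determination, the time from awareness to report is the time to assess plus 24 hours. The first term has no stated limit, so neither does the total.

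These are possibilities that the wording leaves open, not a sequence that it requires.

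**A route with little other review.** Section 7.2 (steps 1.30 and 2.16) sends a subject with a damaged lens back to the site for a replacement, with a complaint form if damage is present. Section 7.3 says that when resupply is the only reason for an unscheduled visit, only dispensing details need be recorded. Such a complaint may be assessed with no AE review at that visit. A visit prompted by symptoms would not qualify for this exception.

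**Later opportunities to catch an event.** Section 7.2 requires AE review and biomicroscopy at Visit 2 (3 ± 1 days after Visit 1, so at most 4 days) and Visit 3 (7 ± 1 days after Visit 2, so at most 8 days). These visits can recover a missed event, but not necessarily within 24 hours or 2 days.

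**The case against.** The strongest reply is that Section 12 describes intake sorting, not medical assessment, and that other duties protect the subject. Much of this stands, and it rules out several stronger readings.

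- A reader might infer that Section 12 builds in a delay: complaint entry, then a call from the COM/CRA, then the AE decision. The text places the assessment at receipt of the complaint and lets site personnel make it. The information requested by the COM/CRA includes any related AE number, so an AE may already be on record. Where a product deficiency may have caused an AE, the complaint and AE procedures run in parallel.
- A reader might infer that a site following Section 12 is led to miss the SAE deadline. Nothing in Section 12 suspends the Investigator's duties in 13.4, or the site's duty, on the Medical Monitor page, to notify the medical monitor within 24 hours of learning of an SAE.
- A reader might infer that a negative answer keeps the event from the Investigator. Section 13.3 requires all adverse events during enrollment to be documented whatever their relationship to the lens, and the scheduled reviews do not depend on a complaint.
- A reader might infer that wholly unmasked sponsor staff control the step. The trial is single-masked, with subjects masked to the lens identity (5.2), and site personnel are one of the three permitted assessors.

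The reply does not remove the conflict over seriousness. Nor does it supply a time limit, the Significant category or a check on negative answers. The surrounding duties help only once someone recognizes the event as adverse, which is the judgment that Section 12 gives to other roles.

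**Conclusion.** The point holds in a limited form. Section 12 states a rule on who decides that conflicts with 13.2 on seriousness and leaves AE versus no AE unreconciled, with no time limit, no Significant category and no confirmation of a negative answer. It is a weakness in safety capture and worth correcting, because the repair costs little.

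Its size cannot be put in numbers: the documents give no complaint rate and no rate of misclassification. A reader might expect the safety conclusions to be at risk, but the two co-primary safety endpoints, Grade 3 or higher slit lamp findings and unacceptable lens fit, come from eye examinations (2.2), and no effect on them is shown. The conclusion rests on reading the list of assessors in Section 12 as alternatives, any one of whom suffices, and on the absence of any other text in the protocol that requires Investigator review of each complaint.

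**What to change.** Reconcile Section 12 with 13.2 and 13.4 by replacing the sentence on who assesses the complaint. The new text should say that:

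- the Investigator, or a clinician at the site to whom this is delegated, makes or confirms the determination of AE, significant AE or SAE for every complaint, including when the answer is that there is none;
- the reporting times in 13.4 run from the site's awareness of the event;
- the COM or CRA only verifies that the determination is recorded, and refers doubts to the medical monitor.

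The cost is a small extra documentation step for the Investigator on each complaint. No new role is needed, because the Investigator already evaluates adverse events under 13.2, and no endpoint, sample size or analysis changes.
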